Overall, study personnel and collecting outcomes data are all experienced in conducting clinical research and are able to engage subjects without causing them distress. If a subject finds the research procedures to be upsetting or aversive, they will have the option to withdraw from the study. Participation will be completely voluntary, and will not affect the treatment they are receiving at the UM/JMMC Adult HIV Outpatient Clinic. Participants will be told that they may choose not to answer any questions and may decide to terminate the interview at any time. Research staff will be instructed to terminate interview sessions if participants appear to be stressed by the process. Additionally, the research staff will know how to link participants immediately with treatment personnel including case managers or therapists if participants appear to be stressed.

Protection for Suicide and Depression Risk: Subjects who become suicidal or psychotic will be withdrawn from the study and offered (or when necessary, involuntarily given) appropriate treatment. Our screening process will include an assessment to identify participants at risk of suicide. Potential participants will be told before screening that a positive screen will lead to disclosure of this information to their primary care provider (PCP) or to a mental health professional to maintain safety. The Paykel Suicide Items 152 will be administered by a trained RA at every baseline and follow up assessment. In the unlikely event that suicidal ideation is detected the following steps will be taken. First, the RA will inform the participant that this information is very important and needs to be shared with his/her PCP or with a mental health professional immediately (as discussed prior to the screener). Second, the RA will then

IRB Study Number: 20181032
Version 8, Date: 07/16/2021

contact the principal investigator (PI) to discuss the situation. Third, the PI will contact the participant's PCP to ensure the participant is evaluated promptly for safety. Fourth, if the PCP is not available, the PI will arrange for transportation to the nearest emergency room. The RA will remain with the participant until the individual is assessed by a mental health professional or ER physician.

If a participant meets criteria for major depressive disorder or an anxiety disorder, the following steps will be taken. First, the RA will seek written permission from the participant to contact his/her PCP or a mental health professional. Second, the RA will contact the PI to discuss the situation. Third, the PI will contact the PCP or a mental health professional informing them of their patient's positive screen. Fourth, the PI will coordinate with the PCP or mental health professional and the participant to set up an appointment.

Protection of Risk of Physical Discomfort: Because the HOLA intervention involves physical exercise, to which some participants may be unaccustomed, we will put several safeguards in place to avoid injury or harm. These safeguards have been used successfully in other studies involving exercise done by [name] (co-investigator). First, the 10 meter walk test will be used to evaluate walking ability. The use of this test is recommended in order to obtain the most valid clinical assessment of walking speed when using it as a 1-time indicator of health status. Second, all participants will be required to have a written medical clearance for participation in the study. In addition, all participants will be evaluated with a set of screening questions to identify individuals who may be at risk of harm from engaging in exercise. We will require these individuals to additionally obtain written recommendations for physical exertion from their physicians specifically responding to the identified health concern before engaging in HOLA. Third, CHWs will work with participants to set exercise goals that are safe and reasonable in relation to their exercise capacity. Furthermore, exercise plans and instructions to participants will be within the accepted range recommended by the American College of Sports Medicine guidelines. Fourth, CHWs will supervise all walks to observe participants' ability to tolerate exercise. CHWs will maintain a list of the phone numbers of the participants' physicians to contact with health concerns about participants. CHWs will be certified in CPR and will have cell phone capacity in the unusual event of a medical emergency. In the case of minor effects of exercise such as muscle soreness, CHWs will be trained to provide advice regarding stretching or other remedies to ameliorate symptoms. If symptoms worsen, the exercise protocol will be modified after discussion with [name].

Protection of Risks During Venipuncture: Blood draws will be performed by certified phlebotomists who routinely perform venipuncture; steps will be taken to diminish the risk of minimal discomfort, bruising, excessive bleeding, clotting, and/or fainting. If subjects have unusual symptoms,

IRB Study Number: 20181032

Version 8, Date: 07/16/2021

pain, or any other problems arising due to venipuncture, they can also contact the CHW or PI directly.

14) Potential Benefits to Subjects*

The potential benefits of the project to the participant is that the participant may acquire and practice health behaviors that lead to a decreased risk of developing cardiometabolic disease. The benefit to society is that the project may help demonstrate the effectiveness of the HOLA health promotion intervention in preventing cardiometabolic disease in HIV-infected patients.

In relation to the anticipated benefits, the risks to the subjects are reasonable in relation to the benefit of not developing a life-threatening cardiometabolic disease. Participants are de-identified to minimize loss of confidentiality; suicidality or severe depressed can be addressed by trained mental health professionals; discomfort during venipuncture is mitigated by trained phlebotomists.

15) Vulnerable Populations*

N/A

16) Multi-Site Research*

This is not a multi-site study.

17) Community-Based Participatory Research*

N/A

18) Sharing of Results with Subjects*

Study results will be published in scientific journals. Individual subject results will not be shared unless the safety of the participant is at risk.

19) Setting

Group walks will be conducted at a public park that is centrally located to the participants. All assessments and blood draws will be conducted in private rooms at the at the UM/JMMC Adult HIV Outpatient Clinic.

20) Resources Available

Department of Psychiatry and Behavioral Sciences

The Department of Psychiatry and Behavioral Sciences offers clinical evaluation and treatment services for a broad range of emotional, cognitive, and behavioral disorders in patients of all ages, socioeconomic levels, and cultural backgrounds. Services are available on an outpatient, inpatient, or partial hospitalization basis and include individual, family, and group approaches. Specialty areas include geriatric psychiatry, anxiety and mood disorders, stress and psychobiologic dysfunction; biofeedback; behavioral medicine; memory disorders; psychopharmacology; alcohol and substance abuse; and women's mental health, among others. The

IRB Study Number: 20181032
Version 8, Date: 07/16/2021

Center on Aging, among others, link other organizations in research, education, and treatment for special populations at risk. The Department's outpatient programs are located in the Jackson Mental Health Hospital Center. Inpatient facilities for children, adolescents, and adults are located at the Jackson Mental Health Hospital Center and the Highland Park Pavilion, as well as the University of Miami Hospital and Miami VA Medical Center. Through its Division of Consultation Psychiatry and Psychosomatic Medicine, the Department provides consultation to all clinical departments as well as programs of illness prevention and long term care management. The Department provides educational and consultative services to the Dade County Jail, the South Florida Evaluation and Treatment Center, and various courts and governmental agencies through its Forensic Psychiatry Program.

Center for Latino Health Research Opportunities (CLaRO)

The NIMHD has renewed support of health disparities research at the SONHS through the Center for Latino Health Research Opportunities (CLaRO; U54MD002266-11). CLaRO, an interdisciplinary center led in collaboration with Florida International University, is funded from 2017-2022. CLaRO's unifying theme is conducting and promoting multi-level community-based participatory research to prevent substance use, violence/trauma and HIV/AIDS syndemic conditions and reduce their adverse health and mental health outcomes. CLaRO's focus is on tailored interventions for Latino subgroups who represent pockets of vulnerability and require precise and specialized interventions that optimize access to and impact of interventions. CLaRO contains two community-based randomized trials of culturally-tailored behavioral interventions: (1) HoMBRES de Familia, which is testing an intervention to prevent HIV, substance abuse and violence among Latino seasonal farmworker fathers and their sons; and (2) Computer Assisted Family Intervention to Treat Self-Harm Disparities in Latinas and Sexual/Gender Minority Youth (CA CIFFTA), which tests a family intervention for Latinas and sexual/gender minority youth. CLaRO also sponsors a Pilot Projects Program, scientific resources, training and mentorship to serve as an engine for the advancement of early-stage investigators and for diversifying the workforce of successful health disparities investigators. The CLaRO theme, agenda and priorities were developed in collaboration with a network of community partners who will play an ongoing role as a Community Advisory Board, in guiding and disseminating CLaRO science and advancing neighborhood capacity building and multilevel interventions to promote health in Latino communities.

As a CLaRO pilot awardee, I will have access to training and mentoring activities throughout the pilot award, which will enhance the success of this proposal. CLaRO keeps a database of common measures for constructs relevant to their studies, which I will utilize for my proposal

IRB Study Number: 20181032

Version 8, Date: 07/16/2021

and will continue to use. I will also benefit from oversight from CLaRO's Investigator Development Core and Executive Committee. As stated in my training plan, I will continue participating in CLaRO's training activities, such as the recent summer training program focused on Latino health disparities research. Finally, I will be part of a cohort of pilot awardees who are also conducting research related to Latino health disparities and we will meet monthly for ongoing support and potential collaboration.

21) Prior Approvals

N/A

22) Confidentiality

This is not a multicenter study. Please see above for information how we will maintain confidentiality.

23) Provisions to Protect the Privacy Interests of Subjects

Participants will sign a statement attesting to their understanding that their information will be kept private and confidential to the extent permitted by law. Participants know that they will be assigned unique case numbers (and their names will not be used) to protect their identity. Participants will be encouraged to ask questions throughout the consent process and will be provided contact information for [name] (PI) and the University of Miami's Human Subjects Research Office. Data will only be available to researchers approved by the IRB and to the study monitoring unit. Participants will be reminded of their ability to stop the interview or refuse to answer questions that make them uncomfortable. During all study procedures (e.g., recruitment, consent process), participants will be assured that their information is confidential and will sign a statement attesting to their understanding that their information will be kept private and confidential to the extent permitted by law.

Participants know that they will be assigned unique case numbers (and that their names will not be used) to protect their identity

24) Compensation for Research-Related Injury

Although risks are unlikely, an injury may occur. If an injury should occur, treatment will in most cases be available. If participants have insurance, their insurance company may or may not pay for these costs. If they do not have insurance, or if their insurance company refuses to pay, they will be expected to pay. Funds to compensate for pain, expenses, lost wages and other damages caused by injury are not routinely available.

25) Economic Burden to Subjects

There are no costs associated with your participation in this study.

IRB Study Number: 20181032

Version 8, Date: 07/16/2021

26) **Consent Process**

For individuals that are interested in the participating in the research study, the study will obtain an informed consent form from the participant. The study will provide the participant a copy of the consent form, and, because the participant may have a low level of literacy, will then read the consent form out loud.

Once the entire consent form has been read and explained, the assessor will give the participant a chance to ask any additional questions. If the participant agrees to participate, they will be asked to sign the informed consent form and will be given a copy of the signed form.

The consent form for participation in the study are submitted within this protocol for approval to the University of Miami Institutional Review Board (IRB) Behavioral Subcommittee for the Protection of Human Subjects.

Non-English Speaking Subjects

Should the need arise, we will translate and back-translate the informed consent forms and submit them to the IRB for approval.

Waiver or Alteration of Consent Process (consent will not be obtained, required information will not be disclosed, or the research involves deception)

N/A

Subjects who are not yet adults (infants, children, teenagers)

N/A

Cognitively Impaired Adults

Cognitively impaired adults will be excluded from this study.

Adults Unable to Consent

Adults who are unable to consent will be excluded from this study.

27) **Process to Document Consent in Writing**

Signed consent will be collected. After the study is explained and the study participant verbally indicates that he or she understands study procedures, the participant will sign and date the consent form. The participant will be given a copy of the signed consent form for his/her records, and the second copy will be stored in a locked office.

28) **Drugs or Devices**

N/A

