needs and circumstances of midlife and older Latinos living with HIV. HOLA builds on prior research using health promotion to prevent depression and anxiety in older Latinos. In the present context, HOLA uses a lay community health worker (CHW) to lead a health promotion program in order to reduce cardiometabolic risk and improve psychosocial functioning and health-related quality of life in midlife and older Latinos living with HIV. Such an approach could appeal to midlife and older Latinos living with HIV as a nonstigmatizing and culturally acceptable intervention. HOLA addresses multiple concerns that are prevalent in this community (cardiometabolic risk, psychological distress). In addition, cultural values and beliefs were included in the formative and development phases of the intervention to ensure that the different socio-cultural influences that have a role in the health of Latinos were incorporated. Thus, HOLA is the optimal choice to address an urgent medical and public health issue, and one that is rapidly growing. The objectives of this pilot study are two-fold: (1) to evaluate the feasibility and acceptability of HOLA among HIV-infected Latinos aged 50 and older and (2) identify modifications needed in the design of a larger, ensuing hypothesis testing study. HOLA, which is informed by Behavioral Activation and Social Learning theory is a CHW-led, multicomponent, health promotion intervention consisting of: (1) a social and physical activation session; (2) a moderately intense group walk led by a CHW for 45 minutes, 3x/week for 16 weeks; (3) pleasant events scheduling. The proposed pilot study will recruit and enroll 18 community dwelling Latinos living with HIV aged 50+. Participants will be assessed at three time points (baseline, post intervention, and 3 months post intervention) on measures of cardiometabolic risk factors (waist circumference, dyslipidemia, hypertension, and glucose), psychosocial functioning, and health-related quality of life. Consistent with recommendations from biostatistical workgroups funded by NIH, this pilot study is not powered to test a hypothesis. Rather, this pilot study is a requisite initial step in exploring an innovative application of the HOLA health promotion intervention.

5) **Inclusion and Exclusion Criteria***

Inclusion Criteria:

The following conditions must be met for study eligibility:

- are Latino (self-identified);
- are age 50+;
- are male;

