- are HIV infected but are virologically suppressed (viral load <200 copies/mL);
- volunteer informed consent
- have medical clearance by a physician;
- expect to stay in Miami for the next 6 months; and

IRB Study Number: 20181032

Version 8, Date: 07/16/2021

- have documented risk of cardiometabolic disease.

Exclusion Criteria:

Individuals meeting any of the following criteria will not be eligible to participate in the study:

- have a diabetes diagnosis;
- at baseline meet criteria for current major depressive disorder or generalized anxiety disorder;
- meet criteria for current alcohol or other substance abuse disorders;
- have a lifetime history of bipolar disorder or other psychotic disorder;
- have a diagnosis of any neurodegenerative disorder or dementia (Parkinson's disease, Alzheimer's, vascular, frontotemporal dementia, etc.) or significant cognitive impairment as indicated by a Mini Mental Status Exam score <24;
- have contraindications to physical activity outlined in the American College of Sports Medicine standards; (g) have high suicide risk i.e., intent or plan to attempt suicide in the near future (a response of "yes" to questions 3, 4, and/or 5 on the Paykel Questionnaire);
- are unable to complete 10 m walk test;
- currently residing in a nursing or group home;
- have a terminal physical illness expected to result in the death within one year;

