In addition, we will also collaborate with another study, the Clinic Registry Project (IRB#20160911), which serves as a consent to contact database, to contact eligible participants. They will provide us with contact information for participants in their study who have consented to be contacted by other studies. When contacting participants, the CHW will follow the phone script for calling UHealth consent to contact participants that has been tailored to this study.

8) **Procedures Involved***

Participants will be assessed at three time points (before starting the study, 4, and 7 months after the first interview) on measures of cardiometabolic risk factors (waist circumference, dyslipidemia, hypertension, and glucose), psychosocial functioning, and health-related quality of life.

All participants will read and sign an informed consent document and a HIPAA Research Authorization – Form B approved by the University of Miami Institutional Review Board (IRB). They will initially be provided with a verbal summary of the study and for those who appear to have problems reading the consent form it will be read aloud. Participant payments will be graduated. Participants will receive \$15 on the first visit, \$25 on the second visit, and \$35 on the third visit (total of honoraria = \$75).

Prior to starting the baseline assessments, blood draws will take place at the UM/JMMC Adult HIV Outpatient Clinic. Study staff will obtain initial HDL-C, LDL-C, triglycerides, insulin, and HbA1c levels via review of the electronic medical records. Trained and certified research assistants (RAs) who have at least a bachelor's degree will conduct all assessments in private offices at the UM/JMMC Adult Outpatient HIV Clinic, at a private interview room at the CTRS located on the 7th floor of the Don Soffer Clinical Research Center, or the participant's home. To ensure privacy in the home, we will conduct the interview in a private room with a door of the participant's choosing away from any common areas. In the event that there are other people in the house, the door can be closed to maintain privacy. In the event that an in-person interview is not feasible then the interview will be

IRB Study Number: 20181032

Version 8, Date: 07/16/2021

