conducted over the telephone. At 4 and 7 months after the initial interview, fasting blood samples will be drawn via venipuncture and stored at 4°C until analysis. HOMA will be calculated, providing a measure of insulin resistance. Study measures will be administered after the blood draws.

Assessment Measures

Cardiometabolic Risk: list of current medications, waist circumference, total cholesterol, HDL-C, LDL-C, triglycerides, blood pressure, and HbA1c, will be used to measure cardiometabolic risk.

Dementia Screen: The Mini Mental Status Exam (MMSE) will be used to screen for dementia. A Mungas-adjusted score of 23 or below indicates cognitive impairment.

Walking Ability: The 10 meter walk test will be used to evaluate walking ability, which has been used as a screening instrument to measure functional mobility and gait speed in physical activity interventions with older adults.

Demographics: The CLaRO Demographics Form will be used to collect demographic information (e.g., gender, education, income, preferred language, country of origin, time in the US, etc.) and will include a list of all diagnosed medical conditions and medications.

Acculturation: The 24-item Bidimensional Acculturation Scale (BAS) will be used to measure acculturation.

Depression Severity: The 20-item Center for Epidemiologic Studies Depression (CES-D) Scale and the 9-item Patient Health Questionnaire (PHQ-9) will be used to measure depression severity.

Anxiety Severity: The 7-item Generalized Anxiety Disorder (GAD-7) scale and the 14-item Perceived Stress Scale will be used to measure anxiety severity.

Social Support: Perceived social support will be measured using the 12-item Multidimensional Scale of Perceived Social Support (MSPSS).

Health Related Quality of Life: The SF-12 will be used to assess for health related quality of life.

Physical Activity: The 16-item Global Physical Activity Questionnaire (GPAQ) will be used to measure physical activity.

Stigma: The HIV Stigma Scale (HSS) is a 40 item measure of stigma and psychosocial aspects of having HIV.

IRB Study Number: 20181032

Version 8, Date: 07/16/2021

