The third component consists of scheduling pleasant events. During the cool down phase of each walking session, the CHW will ask each participant to identify a pleasant event that they intend to do with another person before the next meeting. The CHW will be trained to problem solve (e.g. brainstorming) if a member of the group cannot think of a pleasant event. Subsequent sessions will start with participants reporting on how effectively they implemented their pleasant event plan while the CHW and the group provide positive reinforcement and feedback. This component provides a means to generalize the intervention into the participants' every day lives. Mood ratings will be taken directly before and after each walk so participants can see, in real time, changes in their moods. These motivational tools stem from our qualitative study in which participants reported feeling motivated to engage in health promotion when they received positive reinforcement through clear indicators of progress. Participants will walk at a centrally located public park.

The final component is a maintenance phase consisting of one "booster" walking session twice a month for three months post intervention to reinforce the behavior change and maintain the effects of the intervention. We believe that we are more likely to detect sustained effect if maintenance is provided.

Should unavoidable circumstances arise and in-person meetings are not possible then the CHW will have regularly scheduled phone call with the participants to maintain motivation for increased physical activity and pleasant events.

Management of safety concerns

If a participant meets criteria for major depressive disorder or an anxiety disorder, the following steps will be taken. First, the RA will seek written permission from the participant to contact his/her PCP or a mental health professional. Second, the RA will contact the PI to discuss the situation. Third, the PI will contact the PCP or a mental health professional informing them of their patient's positive screen. Fourth, the PI will coordinate with the PCP or mental health professional and the participant to set up an appointment.

9) **Data and Specimen Banking***

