As a pilot study, we will evaluate the feasibility of recruitment, assessment procedures, retention, acceptability, and implementation of HOLA in a sample of midlife and older Latinos living with HIV (**Aim 1**). Consistent with recommendations from biostatistical workgroups funded by NIH, this pilot study is not powered to test a hypothesis. This approach to analysis of feasibility data mirrors the structure of the first HOLA trial and other pilot trials conducted at the CNSA. Successful recruitment will be defined as meeting 100% of targeted sample (N = 18), with 20% or less of eligible subjects refusing to participate. Adequate retention will be defined as 85% or more of randomized subjects completing the post-intervention assessment. Acceptability is defined as 80% or more of sessions attended by subjects. To identify modifications needed in the design of a larger, confirmatory randomized controlled trial (**Aim 2**), we will use a project evaluation questionnaire developed by investigators at the CNSA and used in previous studies. The items are a mix of rating scales, yes/no questions, and open-ended questions that allow participants to give feedback in short answer format with specific interest in understanding the participants' opinions regarding the specific components of the intervention. To explore changes in cardiometabolic risk factors (waist circumference, dyslipidemia, hypertension, and glucose), psychosocial functioning (depression and anxiety severity, social support), and health-related quality of life (**Aim 3**), a one-way ANOVA will be used to illustrate the change in scores from baseline to post-intervention in all the outcome measures used.

A repeated measures ANOVA, as we have proposed, is appropriate to explore the intervention effects on cardiometabolic risk factors,

IRB Study Number: 20181032

Version 8, Date: 07/16/2021

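### The residence criterion (6 months) ends before the last assessment and fasting blood draw (7 months), so a man who already expects to be away for the third visit is eligible

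*Combined protocol and SAP*

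**What the plan says.** Section 5 (Inclusion and Exclusion Criteria) requires that a man "expect to stay in Miami for the next 6 months; and". No other listed criterion asks for availability beyond that.

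The visit schedule is stated in two ways:

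- Section 8 (Procedures Involved) counts from the first interview: "Participants will be assessed at three time points (before starting the study, 4, and 7 months after the first interview". It gives blood sampling the same timing: "At 4 and 7 months after the initial interview, fasting blood samples will be drawn via venipuncture".
- Section 4 (Background) counts from the end of the intervention: "Participants will be assessed at three time points (baseline, post intervention, and 3 months post intervention". The intervention lasts 16 weeks, and section 8 adds booster walks over the following three months.

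On place and mode of assessment:

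- Section 8 allows assessments at the clinic, at a research centre or in the participant's home. "In the event that an in-person interview is not feasible then the interview will be" done by telephone.
- For the intervention it adds: "Should unavoidable circumstances arise and in-person meetings are not possible then the CHW will have regularly scheduled phone call with the participants".
- Section 19 (Setting) states: "All assessments and blood draws will be conducted in private rooms at the at the UM/JMMC Adult HIV Outpatient Clinic".

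Section 10 (Data Management) sets the retention criterion: "Adequate retention will be defined as 85% or more of randomized subjects completing the post-intervention assessment". For Aim 3 it plans a baseline to post-intervention comparison. It also plans a repeated measures ANOVA, which it defends by the use of that method with three or more time points. Section 6 sets the sample at 18.

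**The concern.** A residence criterion is there to ensure that the men enrolled can be measured at every planned visit. This one stops short of the last visit, so it does not screen out a man who says at enrolment that he will have left by then.

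The data at stake are the third set of fasting blood, waist and blood pressure measurements. That visit is the only assessment after the booster phase, so it alone can show whether any change lasts. The documents name no method for missing data. A standard repeated measures ANOVA uses only participants with all three values, so a man without third-visit measures would also lose his baseline and 4-month values in that analysis. In a sample of 18, each such loss is noticeable, and this source of loss can be avoided by wording.

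**Working it through.** **Inputs.** Required stay: 6 months (section 5). Last visit: 7 months after the first interview (section 8), or 3 months after a 16-week intervention (sections 4 and 8). Sample: 18 (section 6). One month is taken as 365.25/12 = 30.4375 days.

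**Step 1: do the two schedules agree?** 16 weeks = 112 days, and 112/30.4375 = 3.68 months. Adding 3 months gives 6.68 months. These round to the stated 4 and 7 months, so the two descriptions agree to the whole month if walks begin straight after the first interview.

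**Step 2: compare the stay with the last visit.**

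| Quantity | Calculation | Day |
|---|---|---|
| End of required stay | 6 × 30.4375 | 182.6 |
| Last visit, counted from first interview | 7 × 30.4375 | 213.1 |
| Last visit, 16 weeks + 3 months, immediate start | 112 + 3 × 30.4375 = 112 + 91.3 | 203.3 |

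Shortfall on the first timing: 213.06 − 182.63 = 30.4 days. On the second: 203.31 − 182.63 = 20.7 days. On the second timing, any delay in starting the walks adds to the shortfall. Counting the 6 months from consent does not help, because the baseline interview cannot come before consent.

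**Step 3: do the fallbacks fill the gap?** The telephone option replaces an interview, so it could recover the third-visit questionnaires. The telephone calls by the community health worker replace intervention contact. Neither yields blood, waist or blood pressure. Home assessment carries no stated provision for a man who has left Miami, and section 19 places blood draws at the clinic. Section 8 describes use of laboratory values from medical records only for the initial values; at 4 and 7 months it specifies venipuncture.

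**Step 4: size of the loss.** Each man without third-visit physical measures removes 1/18 = 5.6% from the three-time-point analysis of those measures. The counts below are assumed, with no other loss.

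| Men affected | Complete cases | Share of 18 |
|---|---|---|
| 0 | 18 | 100% |
| 1 | 17 | 94.4% |
| 2 | 16 | 88.9% |
| 3 | 15 | 83.3% |

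**Step 5: what is not affected.** The post-intervention visit falls at about month 4, inside the 6 months. The 85% retention criterion and the baseline to post-intervention comparison are therefore untouched, as is the recruitment criterion.

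**Step 6: is 7 months long enough?** On the end-of-intervention timing the stay needed is 203.3 days plus any start delay. Seven months leaves 213.06 − 203.31 = 9.75 days, so it covers a start up to about 10 days after the first interview. The documents give no start delay.

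**The case against.** The best case for leaving the text alone is that little depends on it. Aim 3 is exploratory, the pilot is not powered, and 6 months covers the whole 16-week intervention and the visit at which retention is judged. The criterion concerns staying in Miami; a man who leaves may come back for the visit. Those exposed are only men who already plan, at screening, to leave before the third visit and not return for it. Participants are told about the study before they sign, many receive their HIV care at the recruiting clinic, and the third visit carries the largest payment ($35). All of this stands, and it limits the size of the problem. It does not make a 6-month rule cover a 7-month visit.

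It can also be said that losing a man's earlier values comes from the unstated missing-data method, not from the criterion. That is right: a longer stay would not cure it for visits missed for other reasons. The criterion nevertheless admits a cause of missing data that can be foreseen.

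Finally, a fixed 7 months has little margin. Walks are held in groups of six, each man first has an individual session, and forming groups could take more than 10 days (an inference, since no delay is stated). This also stands, and it favours tying the criterion to the last scheduled visit.

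**Conclusion.** The concern holds. The required stay ends about 30 days before the last visit on the schedule in section 8, and at least about 21 days before it on the timing in section 4. No other criterion or stated remote procedure secures the third-visit blood, waist and blood pressure data.

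The consequence is confined to the third time point of an exploratory analysis. The number of men affected is unknown and could be zero. The 5.6% per man assumes complete-case repeated measures ANOVA and no other loss. The correction should be made because the rule is wrong against the plan's own schedule and is easy to put right; the primary feasibility criteria are not threatened.

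**What to change.** Reword the residence criterion so that a man must expect to remain in Miami through his last scheduled assessment, and for at least 7 months from the first interview.

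As a separate clarification, use one anchor for the visits in sections 4 and 8. A workable choice is to hold the post-intervention assessment after each man's 16 weeks end and the last one 3 months later. On that anchor, a permitted start delay of more than about 10 days needs a stay longer than 7 months. The 3-month assessments mentioned in section 11 have no stated anchor and may be text carried over from the earlier HOLA trial; they should be aligned or removed at the same time.

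The cost is a protocol amendment, which section 11 says needs IRB approval, and possibly a slightly smaller eligible pool against the target of enrolling all 18. The documents give no figure for how many men the longer stay would exclude.
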